
Data Management and monitoring
	
Data systems will be designed to handle the concurrent collection, processing, secure storage, and analysis of project data. New data will be aggregated progressively via a web-based data-entry application (REDCap). Each participant will be assigned a unique number identifying him across waves. The web application will transmit data entered by each participant through an encrypted network connection to a centralized database running on a secure network and infrastructure, ensuring secure electronic data movement. A CCIHP programmer will create, and a CCIHP data manager will run, applications for more refined range/ consistency checks in the centralized database. Systematic data collection errors can be identified, resolved, and documented using a workflow module of the REDCap application. Some statistical software can access data in the central database and store derived variables there. For analyses done with external statistical software, de-identified data will be extracted and held on HIPAA compliant secure networks and computing workstations.

Plans for analysis

[figure not shown]

Descriptive analyses. We will perform univariate analysis of all demographic, screening, mediating, outcome, and control variables for the program and the health-education control groups, individually and combined, to explore distributions, outliers, and missingness. The associations between individual pairs of variables will be examined. Baseline differences on these variables between the program and health-education control condition will be tested. The psychometric properties of the various instruments will be assessed and confirmed.

Intent-to-treat analysis. To assess our aims based on the randomization scheme,¹¹⁴ we will perform mediation analyses via path analysis.^{115,116} Namely, we will assess first whether, relative to men randomized to the health-education control group, men randomized to the program will have improved mediating outcomes (H1). With reference to Figure 2, each of these relationships is represented by path a, or the direct effect of treatment on the mediator. Testing the significance of each path allows us to assess the impact of the program on each mediator. The standardized effect coefficients will serve as effect size measures of the treatment to mediator relations.

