We then will assess the impact of the program on our main outcomes (H2, H3). With reference to Figure 2, each of these relationships is captured by the product of the two paths, ab , or the indirect or mediating impact of the program on our primary outcomes, transmitted through the individual mediators. Testing the significance of each product allows us to assess the significance of each path. To test these mediated effects, we will use confidence intervals derived from the bias-corrected percentile-based bootstrap approach, a resampling technique, as the valid use of regular standard errors relies on the unrealistic normality assumption, given that the products of two normally distributed regression coefficients is not normally distributed in general.^{117,118} A consequence is that the power of the test is reduced.¹¹⁷ The bootstrap approach is suitable here, as it allows researchers to assess the test statistics associated with these mediated effects without knowledge of their true distributions.⁸⁹ The standardized indirect effect coefficients with confidence intervals will serve as effect size measures of the various mediation effects.

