We will test the robustness of the results obtained by investigating potential confounders of paths a and b, which may result in biased estimates. Figure 3 shows how confounders may affect the estimates of relationships between 1) treatment and mediator with tm_1 and tm_2 , and 2) mediator and outcome with mo_1 and mo_2 , which may be biased as a result of omitted or confounding variables.^{117,119} As there will be randomization of the program treatment but not of the mediator variables, most confounders on the treatment-to-mediator relation should be eliminated. Still, we will, perform a balance check on randomization using the control variables listed in Table 5. If imbalance on certain variables is detected, those variables may be controlled for when estimating path a, the program treatment-to-mediator relation. We also will assess the sensitivity of the results to the potential confounders on the mediator-to-outcome relation, path b, using a propensity score approach.^{120,121} The propensity score, or the probability that an individual receives a specified level of the mediator, given a set of observed covariates chosen from Table 5, will be estimated and used as a covariate in the mediation model to estimate path b. The results will be compared to those without any adjustment to detect if possible biases exist due to omitted observed confounders, and if they do, what the directions and magnitude are.

We will perform the intent-to-treat analyses using the software program, Mplus.⁹⁶

Supplemental analyses in the program group. We will conduct several analyses in the program group to assist with the interpretation of findings from the intent-to-treat analyses. First, to gauge possible dose-response relationships between engagement with the program, such as total contact time over the six-session program, and individual post-treatment mediator and outcome variables, we will examine their partial correlations for participants assigned to the program group, adjusting for their corresponding baseline values.¹²² Second, we will assess differential program impact by examining differences in pretest-posttest change scores in mediator and outcome variables across socio-demographic characteristics, such as age, and risk groups, such as alcohol use.

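### The main mediation models name no baseline mediator or outcome score: path-a adjustment is optional and triggered by imbalance, and path b is adjusted only as a sensitivity check

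*Combined protocol and SAP*

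**What the plan says.** All of this is in the combined protocol and SAP, mainly under Plans for analysis.

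- **Main model, H1** (Intent-to-treat analysis): "With reference to Figure 2, each of these relationships is represented by path a". No covariate is named.
- **Main model, H2 and H3** (same section): "each of these relationships is captured by the product of the two paths", tested with bias-corrected bootstrap intervals. Again no covariate is named.
- **Path a, robustness paragraph:** a balance check is run on the control variables of Table 5. Then: "If imbalance on certain variables is detected, those variables may be controlled for when estimating path a".
- **Path b, robustness paragraph:** the plan recognises the difficulty ("As there will be randomization of the program treatment but not of the mediator variables"). Its answer is a propensity score that, "given a set of observed covariates chosen from Table 5, will be estimated and used as a covariate in the mediation model". This is presented as a sensitivity assessment: "The results will be compared to those without any adjustment to detect if possible biases exist".
- **Descriptive analyses**, which cover mediators and outcomes: "Baseline differences on these variables between the program and health-education control condition will be tested". Nothing links these tests to the main models.
- **Supplemental analyses in the program group:** the dose-response correlations are computed "adjusting for their corresponding baseline values". This is the only place where baseline scores are named as covariates.

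Table 2 schedules all primary and secondary outcomes at baseline, posttest and six months. The example confounders under Data collection overview include no baseline mediator or outcome score. Table 2 lists only alcohol use, sexual behavior and sexual communication as control variables.

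**The concern.** There are two problems, and they differ in weight.

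For path a, randomisation protects the estimate. What is lost is the precision a baseline score would give. In addition, the covariate set is left to chance: a variable enters because it happened to differ between arms, not because it predicts the mediator, and even then entry is discretionary.

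For path b, randomisation gives no protection. A man with hostile attitudes before the program is likely to have more hostile attitudes and worse behaviour afterwards, whatever his arm. If the program shifts the mediator, path a is significant, and that pre-existing association in an unadjusted path b then makes ab significant although the program changed no behaviour. H2 and H3 concern the primary outcomes, and the visible text tests them only through ab. The propensity-score comparison might expose the problem, but its covariates are not named in the visible text, and no rule says which result prevails if the two disagree.

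**Working it through.** **Sample size.** 400 men less 30% attrition (Survey sample and power): 400 × 0.70 = 280, or 140 per arm. The plan's power of .80 cannot be reproduced, because the values of a and b, alpha and sidedness are not given. Two-sided .05 is assumed below.

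**Path a.** The plan gives model R-squared values of .13 and .26. Applying .13 to path a is an assumption: d = 2√(R²/(1−R²)) = 2√(.13/.87) = .77. The standard error is √(2/140) = .1195 SD unadjusted. With a baseline score correlating r with follow-up, it is multiplied by √(1−r²). Power from the non-central t:

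| d (R²) | Unadjusted | r = .3 | r = .5 | r = .7 |
|---|---|---|---|---|
| .77 (.13) | >.999 | >.999 | >.999 | >.999 |
| .25 (.015) | .550 | .589 | .673 | .831 |

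Unadjusted power falls to .80 at d = .34 (R² = .027). Baseline adjustment therefore matters for path a only if effects are far below those planned for.

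**Path b.** Assumed: continuous standardised outcomes, n = 280, program effect d = .5 on the mediator, stability .6, baseline mediator–outcome correlation r of .1 to .3, true mediation zero.

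*Autoregressive model* (each follow-up score is .6 times its own baseline plus noise). The unadjusted slope within arm is .6 × .6 × r = .36r. At r = .3 this is .108, with standard error about 1/√280 = .060, so z is about 1.8 and path b is significant in about 44% of trials. Multiplied by path-a power of .986 at d = .5, this gives about 43%. With both baseline scores in the model the expected slope is zero.

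*Stable-trait model* (each score is √.6 × trait plus noise). The unadjusted slope is r itself. With both baseline scores, the normal equations give .4r/(1.6 − 2r²). At r = .3 that is .12/1.42 = .085, so the bias falls from .30 to .085 but does not vanish.

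Simulation (3,000 trials per run, three runs per r, both paths significant) agrees. False mediation:

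| r | Autoregressive, unadjusted | With both baselines | Stable trait, unadjusted | With both baselines |
|---|---|---|---|---|
| .1 | 9.2–9.6% | 4.9–5.4% | 37.4–38.4% | 6.1–7.0% |
| .2 | 22.4–23.4% | 4.9–5.9% | 90.6–91.4% | 13.1–14.5% |
| .3 | 42.6–44.7% | 5.1–5.8% | 97.8–98.6% | 27.9–29.6% |

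**With the planned bias-corrected bootstrap** (400 trials per cell, 400 resamples), at r = .1/.2/.3:

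- Autoregressive: 13.5/31.3/49.8% unadjusted, 4.8/7.3/7.5% adjusted.
- Stable trait: 46.8/93.8/99.0% unadjusted, 11.5/19.0/35.5% adjusted.

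**With a smaller program effect**, d = .25, the unadjusted rates fall to about 4–25% (autoregressive) and 22–55% (stable trait).

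**The planned propensity score.** Modelled at r = .2 to .3 as one covariate correlating .3 to .5 with the baseline scores, it gives 6–25% (autoregressive) and 18–95% (stable trait). It could work well or badly, depending on what goes into it.

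**Binary violence outcome** (thresholded score, linear probability model, r = .2 to .3, both models), unadjusted against adjusted:

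- 2% prevalence (assumed): 7–40% against 5–11%.
- 12%: 11–86% against 4–20%.
- 37%: 17–96% against 6–27%.

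The 12% is women's reported victimization and the 37% is partner violence of any form, so neither is a rate of sexual violence perpetration by men. At the 0.2% that the Background gives for men's reports, .998^280 = .571: 57% of trials of 280 would have no event. The rates above do not apply there, and a baseline perpetration covariate may be constant.

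**The case against.** **The model may be defined in material that cannot be seen.** The paths refer to Figure 2, and the covariates are in Table 5. This is a real limit. But the text ties Table 5 to control variables, which the descriptive section lists apart from mediators and outcomes. Even if Table 5 held the baseline scores, the rule for path a would remain optional and path b would still be adjusted only as a sensitivity analysis.

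**The path-a half has little consequence.** That stands as far as power goes: there is no bias, and no gain at R-squared .13. What remains is that the covariates are not fixed in advance.

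**The plan already recognises confounding of path b and will report its direction and size.** This is to its credit. The gap is that the main result is the unadjusted one and the propensity-score covariates are unnamed.

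**The simulated rates rest on assumed correlations and effect sizes.** That also stands. At d = .25 the inflation is smaller, though in the same direction, and the planned bootstrap shows the same pattern as the joint-significance test.

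**Adjustment is not a full cure.** Under the stable-trait model up to 30% false mediation remains (35.5% with the bootstrap), so the plan should not claim that path b is unconfounded after adjustment.

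**Conclusion.** The concern holds, as a change that should be made. In the visible text the main models for H1 to H3 contain no baseline score, although the scores are collected. For path a the cost is precision at small effects and a covariate set chosen by chance imbalance. For path b the omission can make differences that predate the program look like mediation, and the tests of H2 and H3 rest on that path. The size depends on stability, the baseline mediator–outcome correlation and the program's effect on the mediator, none of which the documents give. Only the direction is firm: adjustment for both baseline scores lowers false mediation, fully in one plausible model and partly in another. Confidence is medium because Figures 2 and 3 and Table 5 were not available.

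**What to change.** Amend the Intent-to-treat section so that, whatever the balance check shows:

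- path a is adjusted for the baseline mediator;
- path b in the main model is adjusted for the baseline mediator and the baseline outcome;
- any total effect is adjusted for the baseline outcome;
- if a baseline perpetration outcome has too few events to estimate, path b is adjusted for the baseline mediator only, with the event cut-off written down before the data are examined;
- the path-b propensity score includes the baseline mediator and outcome scores, under the same exception;
- the balance table is descriptive and does not select covariates;
- the plan states that path b may remain confounded after adjustment.

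If Table 5 or Figure 2 already specifies any of this, a sentence in the text saying so is enough. The cost is SAP wording only, since the baseline scores are already scheduled.

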Bystander self-efficacy	ROLB self-efficacy to intervene in SV ¹⁰¹	When I hear a sexist comment I indicate displeasure	8	1-7
Bystander intervention	ROLB self-behavior subscale ¹⁰¹	walk into my room & roommates are watching porn	5	1-7
Intimate Partner Violence	Revised Conflict Tactics Scale (CTS2) SV ¹⁰²	Used force to make partner have sex	7	1-6
Sexual Violence	Sexual Experiences Survey Rev. (SES-R), SV ¹⁰³	put my penis, fingers, objects into so's butt w/o...consent	8	0-3
Secondary Outcomes (Knowledge, Attitudinal, Emotional Mediators)				
Knowledge of law	Knowledge of legal defs of assault/rape scale ¹⁰⁴	Sex intercourse w/so <16 [is legal if] he/she gives consent	9	T/F
Knowledge of consent	Knowledge of informed consent to have sex ⁶⁸	If a woman dsn't physically resist sex, she has given consent	14	T/F
Norms degrading wn	ROLB other-behavior subscale ¹⁰¹	Rmate suggests...give alcohol to your date to 'loosen her up'	5	1-7
Gender attitudes	Hostility Toward Women Scale ^{105,106}	...many times women flirt w/men just to tease/hurt them	10	T/F
Gender attitudes	Hyper-Gender Ideology Scale short form (HGIS) ¹⁰⁷	If men pay for a date, they deserve smthg in return	19	1-5
Rape attitudes	College Data Rape Attitude & Behavior Survey ¹⁰⁸	...sex jokes and innuendos are only fun & harmless	20	1-5
Rape attitudes	Illinois Rape Myth Acceptance (IRMA) ⁴⁸	Rape happens when a man's sex drive gets out of ctrl	17	1-5
Dating violence attitudes	Attitudes Toward Male Dating Violence Scale ¹⁰⁹	A guy should not insult his girlfriend	39	1-5
Empathy for rape victims	Rape Empathy Scale (RES) ⁵⁴	In general,...rape is not...provoked by the rape victim	19	1-5
Control Variables				
Alcohol use	National College Health Assessment Survey ¹¹⁰	# drinks consumed when last partied	1	#
Sexual behavior	Safe Sex Behavior Questionnaire (SSBQ) ¹¹¹	engage in sex intercourse on the first date	7	1-4
Sexual communication	Communication self-efficacy ¹¹² (to discuss sex)	can discuss...using condoms w/any sex partner	4	1-10
total items and time required			192	42 m

Note. SV = sexual violence; α indicates the reliability of the scale in other samples.

Informed Consent

Assurances, IRB approvals, and oversight: Our ethics protocol will follow WHO guidelines for research on violence against women.¹³¹ Ethical approval will be sought from CCIHP, Emory University, and Georgia State University. Team members have completed certification training in research ethics.

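### The path-b confounding check uses a single-level propensity score for graded mediators, so how much observed confounding it removes depends on a level the plan does not name

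*Combined protocol and SAP*

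**What the plan says.** The relevant text is in the combined protocol and SAP, Quantitative Study Design, Plans for analysis, in the paragraph on robustness of paths a and b.

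- It recognises that path b is observational: "As there will be randomization of the program treatment but not of the mediator variables".
- It defines the adjustment score as "The propensity score, or the probability that an individual receives a specified level of the mediator, given a set of observed covariates", with covariates to be chosen from Table 5.
- The score "will be estimated and used as a covariate in the mediation model to estimate path b".
- Adjusted and unadjusted results are then compared "to detect if possible biases exist due to omitted observed confounders, and if they do, what the directions and magnitude are".

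No level, cut-point, dichotomisation or score model is given there or elsewhere in the text. Table 2 lists the mediators as multi-item scales of 5 to 39 items, answered true/false, 1-5 or 1-7. Examples are "Knowledge of legal defs of assault/rape scale" (9 true/false items), "Knowledge of informed consent to have sex" (14 true/false items) and "Attitudes Toward Male Dating Violence Scale" (39 items, 1-5).

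**The concern.** The probability of one level balances covariates when the exposure has two levels. For a graded mediator it generally does not. Men whose covariates predict low scores and men whose covariates predict high scores can share the same low probability of a mid-range level. A linear term in that probability cannot tell them apart, so the confounding between them stays in path b.

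H2 and H3 are assessed through the product ab, and this is the only analysis described for detecting observed confounding of path b. If the score removes little, adjusted and unadjusted b agree and the comparison looks reassuring, even when every confounder was measured. If it removes part, the comparison flags bias but understates it. Because the level is open, two analysts could also get different answers from the same data.

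**Working it through.** **Inputs from the documents.** The sample is 400 with equal allocation and 30% attrition (Survey sample and power; Field Methods), so completers = 400 × 0.70 = 280. If items are summed, the number of score levels runs from 9 + 1 = 10 for the legal-knowledge scale to 39 × (5 − 1) + 1 = 157 for the dating-violence scale. The documents print no figure for this check, so there is none to reproduce.

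**Assumptions.** The documents give neither confounder strength nor a significance level. I take two-sided 5% and let an index U of observed covariates explain R² = .04, .13 or .26 of both mediator and outcome. The values .13 and .26 are the plan's effect-size benchmarks for power, borrowed here only as a scale. Treatment shifts the mediator by 0.5 SD, the outcome is continuous, and true b = 0.

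**Step 1: unadjusted path b.** With M = 0.5T + √R²·U + error, Y = √R²·U + error, and unit variances within arm, the unadjusted coefficient tends to b = R². The approximate test statistic is t = b√277 / √(1 − b²).

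- R² = .04: t = 0.67, false rejection about 10%
- R² = .13: t = 2.18, about 59%
- R² = .26: t = 4.48, about 99%

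Simulation gives about 10%, 60% and 99%.

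**Step 2: adding a score g(U) as one linear term.** If ρ is the correlation of g with U, the remaining coefficient is R²(1 − ρ²) / (1 − R²ρ²), so the share of bias removed is 1 − (1 − ρ²) / (1 − R²ρ²).

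For the density of M at a level m (in SDs from the mean), g is symmetric in U when m = 0. Then ρ = 0 and nothing is removed. For other m, with φ the normal density:

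- E[g] = φ(m)
- E[Ug] = √R²·m·φ(m)
- E[g²] = N(m; 0, variance (1 + R²)/2) / (2√(π(1 − R²)))

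At m = 0.5 this gives:

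- R² = .26: ρ² = .719, removed = 1 − .281/.813 = 65%
- R² = .13: ρ² = .856, removed = 1 − .144/.889 = 84%

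**Step 3: simulation at n = 280 with estimated scores and five covariates.**

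| Score entered for path b | Observed confounding removed, R² .13 to .26 |
|---|---|
| Density at the mean level | about 0% |
| Density at each man's own level | about 0% |
| Density half an SD off the mean | 65-82% |
| Probability above the 90th percentile | about 62-67% |
| Probability above the 75th percentile | 83-85% |
| Probability above the median | about 92% |
| Fitted mediator mean, or covariates directly | about 98-100% |

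False rejection of b = 0 at R² = .26 is about 99% with no score, the mean-level score or the own-level density. It is 35% with the 90th-percentile cut, 10% with the 75th, and about 5% with the median cut, the fitted mean or direct adjustment. At R² = .13 it is about 60% for the first three, 11% for the 90th-percentile cut, and about 5% for the median cut and for direct adjustment.

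**Step 4: coarser scores and the planned bootstrap.** In a large simulated population, a 157-level score at R² = .13 again shows 0% removed at the middle level, rising to 98-99% at some off-centre levels. A 10-level score is not left wholly unadjusted: its two middle levels remove 49% at R² = .13 and 26% at R² = .26. With the plan's bias-corrected bootstrap (10 levels, R² = .13, three covariates, 250 runs), false mediated effects were 73% unadjusted, 27-30% with the middle level, 72% with the own-level density and 9% with direct adjustment.

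**The case against.** **The check is a comparison, not a significance test on adjusted b.** A cut at the 90th percentile still lowers b by about 62-67%, and a reader would see that as confounding. This stands. The rejection rates under cuts are therefore not failures to flag bias. What fails there is the reported magnitude, which is too small.

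**Zero removal needs particular readings.** It takes the centre of a fine, symmetric score, or the density at each man's own level. The second fits the plan's wording less well. A probability of scoring above a cut is a natural reading, and there removal was never zero. The score model matters too: for a 10-level score, a logistic model for one level removed most of the confounding with one covariate, but only about 11% at the middle level with ten covariates (R² = .13). This also stands, and it shows that the answer turns on choices left open.

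**The 99% figure is near a worst case.** It uses one shared covariate index for mediator and outcome. If the two indices correlate 0.5, b at R² = .26 falls to 0.5 × .26 = .13, and unadjusted false rejection drops to about 57%. For a binary outcome at an assumed 5% prevalence, a linear approximation gives 18% at R² = .13 and 54% at R² = .26. The 99% should not be carried over to H3.

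**Table 5, Figure 3 and the cited propensity-score sources could not be read here.** They may hold more detail. The definition as written is nevertheless the single-level one.

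A reader might infer that the check is useless, or that the trial's mediation findings would be false. The documents do not support either. Some choices the wording allows work well, and the check is a sensitivity analysis beside the planned test of ab.

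**Conclusion.** The point holds as a weakness in a sensitivity analysis that should be corrected. The score defined is suited to a two-level exposure and is applied to graded mediators. Depending on the unstated level, it removes from about 0% to nearly all of the observed confounding. The check can understate the bias it is meant to size and, under the central-level or own-level reading, can wrongly suggest robustness.

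The size rests on assumed confounder strength, a shared covariate index, a continuous outcome and a 5% level. At R² = .04 there is little to miss, since unadjusted false rejection is only about 10%. At R² of .13 to .26 a median cut is roughly adequate. The primary ab test is unchanged by this point, and unobserved confounding is untouched under any version of the score.

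**What to change.** In the robustness paragraph of Plans for analysis, replace the single-level probability. Estimate the adjusted path b by entering the observed covariates directly in the outcome equation of the Mplus path model. If one summary score is preferred, use the fitted mean of the mediator given those covariates. Name the chosen form in advance and keep the planned comparison with the unadjusted b.

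This takes one or two sentences and uses the same data and software. Direct adjustment costs a few degrees of freedom out of about 280.
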